The principal Investigator will conduct a chart review of the methadone doses that participants receive in the 3-month period before the study, between Months 3 and 6 of the study, and between Months 9 and 12 of the study. The review of methadone doses will calculate the number of doses participants received and took home with them instead of receiving at the clinic. In addition to a review of methadone doses, the principal investigator will document results of the urine toxicology tests for the participants in the 3-month period before the start of the study and monthly during the study. Participants will complete two surveys at Day 0, Month 6, and Month 12 of the study: the OUD Checklist, which rates opioid use disorder symptoms based on the DSM-5 criteria, and the SF-36, which measures quality of life. At Months 6 and 12, participants will complete qualitative interviews to determine how the vouchers and social work assistance impacted their financial and social well-being, and whether the SASH Intervention was useful in combating homelessness. Data on the methadone doses, urine toxicology tests, surveys, and qualitative interviews will be stored in a password-protected database.

The principal investigator will calculate the percentage of days participants are homeless during the 6-month period when vouchers are distributed and at Month 12 of the study. The percentage of days participants are homeless will be calculated from data collected by the member of the clinic social work team. These data will be stored in a password-protected database. If there are concerns for the well-being of any of the participants in the study, including if a participant expresses thoughts to harm their self or others, then the principal Investigator [name], a board-certified psychiatrist, will be notified to address the situation. If there are medical concerns, one of the study Investigators [name], a Family Medicine physician, will be notified to address the situation. If the situation involves a potentially life-threatening emergency, then the participant will be sent to the Emergency Department.

2 * Describe all procedures already being performed for diagnostic or treatment purposes (If not applicable to the study, enter "N/A"):

All the participants will be currently receiving methadone for opioid use disorder treatment at the Addiction Treatment Program.

3 * Describe the duration of an individual participant's participation in the study:

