Participants will participate in the study for 12 months.

4 * Describe the amount of time it will take to complete the entire study:
The study will take 15 months to complete the study and data analysis.

5 * Describe any additional participant requirements:

Participants will be recruited for the study if they are receiving methadone from the Addiction Treatment Center at the University of Maryland and are struggling with homelessness, which will be defined as living in an emergency shelter or a place not meant for habitation instead of a fixed, regular, and adequate nighttime residence for at least 15 of the 30 days preceding the first month of the study.

HP-00100771

Sample Size and Data Analysis_V2

Sample Size and Data Analysis

If you uploaded a separate research protocol document in the 'Research Protocol' page, cite the applicable section and page numbers from that document in the answer boxes below.

- 1 * Provide the rationale and sample size calculations for the proposed target population:
The study will recruit eight participants. This is a feasibility study, so the results will be used as pilot data to apply for a larger grant.
- 2 * Provide the plan for data analysis. Include in the description the types of comparisons that are planned (e.g., comparison of means, comparison of proportions, regressions, analysis of variance, etc.), which is the primary comparison/analysis, and how the analyses proposed will relate to the primary purposes of the study:
All the participants in this study will receive the intervention. The participants will not be compared with a matched control group. Comparisons of the percentages of missed and take-home methadone doses will be completed in the 3-month period before the study, between Months 3 and 6 of the study, and between Months 9 and 12 of the study. Comparisons will be completed of the results of the urine toxicology tests in the 3-month period before the start of the study and each month during the study. Comparisons will be completed for the OUD Checklist and SF-36 scores at each of the three time points. The analyses will determine how the study interventions impacted outcomes for opioid use disorder treatment, quality of life, and housing.

ID: VIEW4E02000052800
Name: v2_Sample Size and Data Analysis

HP-00100771

Sharing of Results_V2

Sharing of Results

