Loss of Privacy: The informed consent process, meetings with the social workers, surveys, and interviews will take place in a private and closed office at the Addiction Treatment Program to protect the privacy of the participants. Only the participant and staff associated with the study will be present in the office. If there is any concern that this location is not sufficiently protecting the privacy of the participant, then the meeting will end until another location can be found to protect the privacy of the participant.

Participant Discomfort: Participants could feel uncomfortable responding to the surveys and interviews they will be asked to complete. Participants will be informed that they can choose not to answer any question or share any information that makes them feel uncomfortable during the surveys and interviews.

ID: VIEW4E1b62500F000
Name: V2_Research Related Risks

HP-00100771

Potential Benefits_V2

Potential Benefits and Alternatives

If you uploaded a separate research protocol document in the 'Research Protocol' page, cite the applicable section and page numbers from that document in the answer boxes below.

- 1 * Describe the potential direct benefit(s) to participants:
Many individuals receiving methadone for opioid use disorder are homeless and lack the resources to obtain housing, a predicament that negatively impacts their medical and opioid use disorder care. By obtaining the housing vouchers for temporary housing and social work assistance, these individuals could experience improvements in their opioid use disorder and methadone treatment, quality of life, and housing.
- 2 * Describe the importance of the knowledge expected to result from the study:
While previous studies have shown the benefits of providing permanent housing to individuals receiving methadone for opioid use disorder, none have investigated the benefits of providing temporary housing and social work assistance to these individuals. The potential benefits of these interventions could include improvements in their opioid use disorder and methadone treatment, quality of life, and housing. The data from this study would be written in a manuscript and used as pilot data to apply for a larger grant.
- 3 * Describe how the potential risks to participants are reasonable in relationship to the potential benefits:

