All meetings with the participants will be held in a private office located at the Addiction Treatment Program. Information gathered from these meetings will only be disclosed to staff involved in the study. Electronic data from the study would be stored in a password-protected database to protect the participant's information. Any physical data would be stored in a locked cabinet in a secure location that could only be accessed to by study staff.
- 2 * Describe the location where potential participants will receive research information and detail the specific actions the study team will take to ensure adequate privacy areas:
All study interactions with participants will take place in a private office located at the Addiction Treatment Program. The office will be closed, with only staff and the participant present in the room.
- 3 * Describe potential environmental stressors that may be associated with the research:
There are no potential environmental stressors associated with this research.
- 4 * Will this study have a site based in the European Union?
 Yes No
- 5 * Will the study have planned recruitment or data collection from participants while they are located in the European Union?
 Yes No

Access link below for information about the EU General Data Protection Regulations to assist in answering these questions.
<https://www.umaryland.edu/oac/general-data-protection-regulation/>

ID: VIEW4E1B526087C00
Name: v2_Privacy of Participants

HP-00100771

Confidentiality of Data_V2

Confidentiality of Data

- 1 * Will stored research data contain identifiers or be able to be linked to and identify individual participants (either directly or through a code/research ID)?
 Yes
 No, the data will be stored de-identified/anonymous (stripped of all identifiers, no way to identify individual participants)
- 2 * Where will research data be kept (address electronic and paper data as applicable)? (If this is a VA study please list specific sites that data will be kept.)
Electronic data will be stored and secured in a password-protected database. Any physical data will be stored in a locked cabinet in a locked room at the Addiction Treatment Program. This cabinet will be accessible only to study staff.
- 3 * How will such data be secured?
Electronic data will be stored in a password-protected database accessible only to staff associated with the study. Physical data will be stored in a locked cabinet in a locked room at the Addiction Treatment Program.

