If SSNs are going to be used, describe the specific use and type of SSN to be used (real, scrambled, last 4 digits).

The PHI in this study will be used to obtain information about methadone dosing, results from the urine toxicology tests, and how to contact participants. Addresses will be collected when participants obtain housing so that staff can contact participants if necessary. Email addresses will be collected from participants who have these as a means of contacting them during the study. Social Security Numbers would be obtained so members of the clinic social work team can help the participants apply for government benefits or permanent-housing vouchers.

3 * What Is the source(s) of the PHI?

The sources of the PHI will be from the participants; Methasoft, the software the Addiction Treatment Program uses to document methadone doses for its patients; and Epic, the electronic medical record the Addiction Treatment Program uses to store contact information and results of the urine toxicology tests.

4 * Provide written assurance that Protected Health Information will not be reused. (Note: this refers to re-use on another study or for a purpose which has not been approved, not to the re-use of screening data during the current study).
Protected Health Information will not be reused for purposes outside the scope of this study.

5 * How will permission to allow the use/disclosure of the individual's protected health information (PHI) be obtained? (Choose all that apply:)

- Obtain written authorization (*upload authorization form at the end of the application under "Consent and HIPAA Authorization Forms"*)
- Requesting waiver/alteration of authorization (includes waiver of authorization for recruitment only)
- Qualifies as a limited data set (LDS)

5.1 If you are using a limited data set (LDS), please attach the Data Use Agreement (DUA):

Name _____ Date _____

Modified Date

There are no items to display.

Informed Consent Process

If the study does not involve interaction with participants or a waiver of consent is being requested , answer "N/A" to the questions below.

1 *Indicate the type(s) of consent that will be involved in this study: (check all that apply)

- Not applicable (study may qualify as exempt)
- Request to Waive Consent/Parental Permission (Consent is not being obtained)
- Request to Alter Consent (Some Elements of Consent Waived)
- Request to Waive Documentation of Consent (Verbal/Oral Consent)
- Written Consent Form

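### Surveys and interviews are planned only at the clinic, and the plan states no way to obtain the Month 6 and Month 12 assessments from a participant who cannot come in

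*Combined protocol and SAP*

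**What the plan says.** Two sections fix the place of data collection.

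- Privacy of Participants, item 1: "All meetings with the participants will be held in a private office located at the Addiction Treatment Program". Item 2 goes further: "All study interactions with participants will take place in a private office located at the Addiction Treatment Program".
- Research Related Risks, item 1, under loss of privacy, names the instruments: "surveys, and interviews will take place in a private and closed office at the Addiction Treatment Program". If the office does not protect privacy well enough, "then the meeting will end until another location can be found to protect the privacy of the participant".

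The assessments concerned are set out in Study Procedures, item 1: "Participants will complete two surveys at Day 0, Month 6, and Month 12 of the study" (the OUD Checklist and the SF-36), and "At Months 6 and 12, participants will complete qualitative interviews". Surveys/Questionnaires also lists the Homeless Days Review Form. Under Behavioral Intervention, the clinic social work team administers the homeless-days survey, and that team's meetings are at the clinic.

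Protected Health Information, item 2, provides for off-site contact: "Addresses will be collected when participants obtain housing so that staff can contact participants if necessary". Email addresses are collected for the same purpose. Neither is described as a route for collecting outcome data.

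Withdrawal of Participants, item 3, keeps the data of removed participants in the analysis. It does not say whether they are assessed after removal.

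**The concern.** Four sources of information depend on a participant being in the clinic office: self-reported OUD symptoms, quality of life, days homeless, and the participant's account of whether the intervention helped. Together they carry most of what the study will say about quality of life, housing and usefulness.

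The participants least likely to be in that office at Month 6 or 12 are unlikely to be a random subset. The background section itself says that homelessness raises the risk of discontinuing treatment. The withdrawal section anticipates stopping methadone at the clinic, entering treatment linked to housing, and missing more than half of the meetings. If follow-up data come only from those still able to attend, the results describe a selected group. There is no control group in which a similar loss could be seen, and the results are intended as pilot data for a larger grant application.

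**Working it through.** **Inputs from the documents**

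- Sample size: "The study will recruit eight participants" (Sample Size and Data Analysis, item 1). There is one arm, and no dropout allowance, effect size, alpha or power is stated.
- Interviews: two per participant, 30 minutes each, eight hours in total (Interviews, item 3).
- Analysis: scores are compared at the three time points; no test or pairing is specified (Sample Size and Data Analysis, item 2).
- Non-attendance rate: not given, so a range is assumed below.

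**Step 1. The plan's own figure.** 8 participants × 2 interviews × 0.5 h = 8 h. This reproduces the stated total exactly. It assumes that all 16 follow-up interviews take place.

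**Step 2. The location rule set against the possible reasons for absence**

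| Situation at Month 6 or 12 | Route stated in the plan |
|---|---|
| Can attend the clinic | Clinic office |
| Attends, but the office is not private enough | Another location |
| Cannot attend the clinic | None stated |
| Removed by the investigators | Existing data kept; later assessment not addressed |
| Methadone doses, urine toxicology | Methasoft and Epic records; no office interaction needed to abstract them |

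**Step 3. Weight of one absence.** 1/8 = 12.5% of the sample at that visit.

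**Step 4. Effect on a within-person mean change.** Let m participants be absent, with mean change D_a, and let the others have mean change D_p. The mean change over all eight is ((8 − m)/8)·D_p + (m/8)·D_a. The completers' figure D_p differs from it by (m/8)·(D_p − D_a). For m = 1, 2 and 3, that is 12.5%, 25% and 37.5% of the gap between the two groups. The gap is unknown. If absence is unrelated to change, it is zero on average.

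**Step 5. Effect on precision.** The 95% half-width for a mean change is t(0.975, n − 1)/√n in SD units. The smallest attainable two-sided exact signed-rank p is 2/2^n. The plan names neither method; they serve only as a gauge.

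| Assessed (n) | Half-width (SD) | Smallest p |
|---|---|---|
| 8 | 0.84 | 0.008 |
| 7 | 0.93 | 0.016 |
| 6 | 1.05 | 0.031 |
| 5 | 1.24 | 0.063 |
| 4 | 1.59 | 0.125 |

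With three or more absent, p < 0.05 is out of reach for that test, whatever the data show.

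**Step 6. How likely absences are.** Assume independent non-attendance with probability d at a given visit. Then P(at least 1 absent) = 1 − (1 − d)^8, and P(at least 3 absent) is the binomial tail.

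| Assumed d | At least 1 absent | At least 3 absent |
|---|---|---|
| 0.1 | 0.570 | 0.038 |
| 0.2 | 0.832 | 0.203 |
| 0.3 | 0.942 | 0.448 |
| 0.4 | 0.983 | 0.685 |

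Even at the lowest assumed rate, a visit with someone missing is more likely than a complete one.

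**The case against.** A reader might infer that the plan bars off-site collection, so that data from absent participants cannot be collected at all. The documents do not go that far. The location sentences answer form items about privacy and do not set a rule for absent participants. The plan also has investigators try to re-engage those who miss meetings, and someone who has moved or stopped attending could return for an assessment. What stands is the silence: only in-clinic collection is described, the exception is for privacy, and nothing covers inability to attend.

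A reader might also attribute all such loss to the location rule. For participants who stop methadone at the clinic, enter treatment linked to housing, or miss too many meetings, possible withdrawal is a separate and more direct cause. A telephone option alone would not recover their data.

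It may also be tempting to state a definite false improvement in mean score. That would need an unpaired comparison of all eight at Day 0 with the completers at follow-up, and score differences that the documents do not give. If nobody changes, a within-person comparison of the completers gives zero.

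The plan has real mitigation. Participants must expect to stay in treatment at the clinic for at least a year, selection favours likely attenders, meetings are at least monthly, and $40 is paid at each follow-up. In-clinic assessment is a sensible default for this group. None of this reaches someone who physically cannot come. In a feasibility study, failure to complete follow-up is itself informative, but only if it is counted and reported.

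Finally, the interview guide, homeless-days form and consent form are not in the text reviewed and may state a mode of administration.

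**Conclusion.** The point holds in a limited form. As written, the plan has no route for obtaining the Month 6 and Month 12 self-report assessments from a participant who cannot attend the clinic. Each such participant is 12.5% of that visit's sample, and the resulting bias in a mean change is that fraction of an unknown gap between those present and the one absent. That the loss is related to outcome is probable from the protocol's own account of this population, but it is not demonstrated. The non-attendance rates of 10% to 40%, and their independence, are assumptions. Outcomes taken from dosing and toxicology records are outside the point. This is an inexpensive improvement to a stated rule and does not undermine the design.

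**What to change.** 1. In Privacy of Participants (items 1 and 2) and Research Related Risks (item 1), make the clinic office the default. Allow the Month 6 and Month 12 OUD Checklist, SF-36, homeless-days form and interview to be done by telephone or at another private place when the participant cannot attend. Require a privacy check at the start, and record and report the mode.
2. In Withdrawal of Participants, item 3, state that participants removed by the investigators are still offered these assessments if they agree. The grounds for removal need not change.
3. In Sample Size and Data Analysis, item 2, state that scores are compared within person and that the number assessed is reported at each visit.

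A separate analysis by mode is not worth adding: with perhaps one or two off-site responses among eight, it could not separate a mode effect from chance.

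Cost: a wording change to the protocol and consent form. Existing staff and the contact details already collected would suffice. The downside is a possible difference between telephone and in-person answers, which recording the mode makes visible but does not remove.

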1.2 If No, who is responsible for payment?

2 * Who is responsible for the uncovered research-related costs?

Participant
 Sponsor
 UM
 Other
 There will be no uncovered research-related costs

2.1 If Other, specify:

3 If the participant is responsible for any research-related costs, identify and estimate the dollar amount:

ID: VIEWME1B5D9641800
Name: v2_Research Related Costs

HP-00100771

Compensation for Research Related Injury_V2

Compensation for Research-Related Injury

1 * Is this study under a master agreement that includes a provision requiring the sponsor to provide compensation to participants for research-related injury?

Yes No

1.1 If Yes, please provide the date and title of the agreement and upload the portion of the contract language relevant to compensation for research-related injury:

Name	Created	Modified Date
------	---------	---------------

There are no items to display

1.2 If No (the study is not under a master agreement), is there proposed contract language concerning payment to participants for treatment in the event of a research-related injury?

Yes No

1.2.1 If Yes, indicate the status of the contract review/approval with the ORD and upload the proposed language relevant to compensation for research-related injury:

Name	Created	Modified Date
------	---------	---------------

There are no items to display

ID: VIEW4E1B629EEC000
Name: v2_Compensation for Research-Related Injury

HP-00100771

Payment to Participants_V2

Payment/Reimbursement to Participants

1 * Will participants receive payment (money, gift certificates, coupons, etc.) or reimbursement for their participation in this research?

Yes No

ID: VIEW4E1C52A6D7800
Name: V2_Payment to Participants

Payment/Reimbursement Detail

You indicated that participants will receive payment (money, gift certificates, coupons, etc.) or reimbursement for their participation in this research.

1 * Payment/reimbursement to participants will be for: (check all that apply)

- Travel
- Parking
- Meals
- Lodging
- Time and effort
- Other

1.1 If Other, specify:

2 * What is the total dollar value of the payments/reimbursements over the duration of the study? **Total payment(s) for participation in research of \$600 or more in a calendar year is required to be reported on an IRS Form 1099.**

\$80

3 * Describe the timing and distribution plan for the payment/reimbursement (schedule, means, etc.)?

The participants will receive \$40 in either cash or check each time they complete the surveys and qualitative interview at Month 6 and 12 of the study. The maximum direct compensation each participant can receive during the study is \$80.

4 * Method(s) of payment/reimbursement to be Used:

- Cash
- Check
- Money Order
- Gift Certificate/Gift Card
- Other

4.1 If Other, specify:

ID: VIEW4E1C54A8AC000
Name: V2_Payment Detail

HIPAA (Health Insurance Portability and Accountability Act)

1 * Are you affiliated with, or will you be accessing data from a HIPAA-covered entity? A covered entity might be a hospital, a physician practice, or any other provider who transmits health information in electronic form.

• At UMB, this includes UMB schools designated as covered entities (School of Medicine and School of Dentistry) and entities under the University of Maryland Medical System (UMMS). The Baltimore VA Medical Center is also a covered entity.

• If you are a researcher from any school that is not a covered entity but is accessing electronic medical records from a covered entity (such as UMMC), HIPAA would be applicable. Please see a list of covered entities included under UMMS here: [executed-ace-designation-042018.pdf](#)

Yes No

2 * If Yes, will the study view, access, share, collect, use, or analyze health information that is individually identifiable under HIPAA?

Yes No

ID: VIEW4E1B0A2114400
Name: V2_HIPAA

Protected Health Information (PHI)

You indicated that HIPAA applies and the study will view, access, share, collect, use, or analyze health information that is individually identifiable.

1 *Which PHI elements will be used or disclosed in this study? (Check all that apply)

- Name
- Address (if more specific than Zip Code)
- Dates
- Ages over age 89
- Telephone numbers
- Fax numbers
- Email addresses
- Social Security numbers
- Medical record numbers
- Health plan beneficiary numbers
- Account numbers
- Certificate/license numbers
- Vehicle identifiers and serial numbers, including license plate numbers
- Device identifiers and serial numbers
- Web universal resource locators (URLs)
- Internet protocol (IP) address numbers
- Biometric identifiers, including fingerprints and voiceprints
- Full-face photographic images and any comparable images
- Any other unique identifying number, characteristic, or code, unless otherwise permitted by the Privacy Rule for re-identification
- None

2 * Why is the PHI necessary for this research?

If SSNs are going to be used, describe the specific use and type of SSN to be used (real, scrambled, last 4 digits).

The PHI in this study will be used to obtain information about methadone dosing, results from the urine toxicology tests, and how to contact participants. Addresses will be collected when participants obtain housing so that staff can contact participants if necessary. Email addresses will be collected from participants who have these as a means of contacting them during the study. Social Security Numbers would be obtained so members of the clinic social work team can help the participants apply for government benefits or permanent-housing vouchers.

3 * What Is the source(s) of the PHI?

The sources of the PHI will be from the participants; Methasoft, the software the Addiction Treatment Program uses to document methadone doses for its patients; and Epic, the electronic medical record the Addiction Treatment Program uses to store contact information and results of the urine toxicology tests.

4 * Provide written assurance that Protected Health Information will not be reused. (Note: this refers to re-use on another study or for a purpose which has not been approved, not to the re-use of screening data during the current study).
Protected Health Information will not be reused for purposes outside the scope of this study.

5 * How will permission to allow the use/disclosure of the individual's protected health information (PHI) be obtained? (Choose all that apply:)

- Obtain written authorization (*upload authorization form at the end of the application under "Consent and HIPAA Authorization Forms"*)
- Requesting waiver/alteration of authorization (includes waiver of authorization for recruitment only)
- Qualifies as a limited data set (LDS)

5.1 If you are using a limited data set (LDS), please attach the Data Use Agreement (DUA):

Name _____ Date _____

Modified Date

There are no items to display.

Informed Consent Process

If the study does not involve interaction with participants or a waiver of consent is being requested , answer "N/A" to the questions below.

1 *Indicate the type(s) of consent that will be involved in this study: (check all that apply)

- Not applicable (study may qualify as exempt)
- Request to Waive Consent/Parental Permission (Consent is not being obtained)
- Request to Alter Consent (Some Elements of Consent Waived)
- Request to Waive Documentation of Consent (Verbal/Oral Consent)
- Written Consent Form
- Electronic Consent

2 * Describe the Informed Consent process in detail:

The participants will be brought to a private office at the Addiction Treatment Program (ATP). A designated study member will discuss the purpose and brief synopsis of the study to the participants as well as a discussion of the potential risks and benefits of participant in the study. The approved study member would conduct the Informed Consent with the participant and will allow the participant to ask questions to ensure they understand the information explained to them. After the Informed Consent has been discussed and the participant has asked their questions about the study, the participant will sign the Informed Consent Form.

3 * Confirm that the consent process will explain the following:

- The activities involve research.
- The procedures to be performed.
- That participation is voluntary.
- The name and contact information for the investigator.

Yes No

4 * Describe who will obtain Informed Consent:

An approved study team member would obtain Informed Consent.

5 * If obtaining consent from a legally authorized representative (LAR), describe how you will confirm that the individual is the LAR and can provide legally effective Informed consent. (Answer "N/A" if not obtaining consent from LARs)

N/A

6 * Describe the setting for consent:

The consent process will take place in a private office located at the ATP.

7 * Describe the provisions for assessing participant understanding:

The designated study member conducting the Informed Consent will ask questions to ensure the participant understands the information explained to them. The participant will be provided an opportunity to ask any questions during the process.

8 * Describe the consideration for ongoing consent:

Participants can withdraw their consent to participate in the study at any time. Participants will be informed if there are any changes in the risks of participating during the study. If participants decide to withdraw their consent, they will be informed that the treatment they receive at the Addiction Treatment Program will not be affected.

Consent and HIPAA Authorization Forms - Draft

1 Upload all of your Consent Forms for approval. Use only Microsoft Word.

Name	Created	Modified Date
 SASH Informed Consent Form(0.01)	6/26/2023 8:28 AM	6/26/2023 8:28 AM

IMPORTANT NOTE: the above list of consent forms (if any) are DRAFT versions. Under no circumstances should copies of these be distributed to patients/study subjects. If/when this research submission is approved by the IRB, approved consent forms will be available for download and use from the "Documents" tab of the Submission's workspace (click Exit and then look for the Documents tab - approved submissions only)

1A Archived Consent Forms:

Name	Created	Modified Date
 SASH Informed Consent 06142023.docx(0.01)	6/14/2023 10:34 AM	6/14/2023 10:34 AM
 Informed Consent Form(0.02)	7/7/2022 9:34 PM	7/11/2022 8:21 AM

2 Upload any HIPAA authorization forms here:
There are no items to display

Please refer to HRPO's website for specific instructions for preparing informed consent documents and to access current templates: <http://hrpo.umaryland.edu/researchers/consents.html>

ID: VIEW4E1C7712D3000
Name: v2_Consent Forms - Draft

Organization Review Requirements (other than IRB)

Answer the following questions to determine additional organizational review requirements:

1 **Department/Division Review** - All research submissions are required to undergo department/division/institutional review prior to IRB review. The following entity is listed as the required department/division/institutional review:

Psychiatry

If this information is incorrect, please notify the HRPO office.

2 **RSC Review Criteria** - select 'Yes' If the answer is 'Yes' for any of the following questions. Review by the Radiation Safety Committee may be required.

* 2.1 Does the research involve the use of ionizing radiation?

Yes No

2.2 Does the research involve the sampling of radioactive human materials for subsequent use or analysis in a laboratory?

3 **IBC Review Criteria** - select 'Yes' If the answer is 'Yes' for any of the following questions. Review by the Institutional Biosafety Committee may be required.

* 3.1 Does the research involve human gene transfer?
-OR-

Yes No

Does the research specifically apply to human studies in which induction or enhancement of an immune response to a vector-encoded microbial immunogen is the major goal, and such an immune response has been demonstrated in model systems, and the persistence of the vector-encoded immunogen is not expected? This type of research is often referred to as recombinant vaccine trials.

3.2 Does the research involve the exposure of human subjects to pathogenic microorganisms, or the exposure of research staff to human subjects or samples known or reasonably expected to carry infectious disease(s)?

3.3 Does the research involve the sampling of materials from persons with no known infectious disease and where the only risk to study staff is occupational exposure to bloodborne pathogens as defined by the OSHA Bloodborne Pathogen Standard?

4 **Cancer Center Criteria** - Answer the following to determine if review by the Cancer Center (Hematology-Oncology) may be required.

* Does the protocol involve in any way studies related to the prevention, treatment, diagnosis, or imaging of neoplastic diseases?

Yes No

5 **General Clinical Research Center Review Criteria** - the GCRC offers free and/or cost shared resources for patient-oriented research. Click Here for more information.

Answer the following to determine if review by the GCRC may be required.

* Will the General Clinical Research Center (GCRC) facility or resources be used to conduct this activity?

Yes No

6 **VA Review Criteria** - Answer the following questions to determine if review by the VAMHCS R&D Committee may be required.

* 6.1 - Will the research be conducted by VA Investigators including PIs, Co-PIs, and Site Investigators on VA time (serving on compensated, WOC, or IPA appointments)?

Yes No

* 6.2 - Will the research utilize VA resources (e.g., equipment, funds, medical records, databases, tissues, etc.)?

Yes No

* 6.3 - Will the research be conducted on VA property, including space leased to and used by VA?

Yes No

PLEASE NOTE that the research may be funded by VA, by other sponsors, or may be unfunded.

Summary of Required Reviews (other than IRB)

1 Additional Committee Reviews - Based on your responses to the previous questions, you have identified the following additional reviews. To complete or view these additional committees' forms, click on the links below or exit this application and click on the appropriate button on left side of this submission's webpage.

Name of Related Submission

This protocol has no related submissions (RSC, GCRC, IBC, etc)

